The Screening and study visits will be conducted in the same fashion as described above for Cohort 1. Approximately sixty-three (63) subjects will be randomized to 2.0% AXR-270 Cream or its Vehicle.

	
Study Schematic (Cohort 1):
  
The diagram illustrates the study timeline for Cohort 1. It shows five visits: Visit 1 (Screening), Visit 2 (Day 1, Randomization), Visit 3 (Day 8), Visit 4 (Day 15), and Visit 5 (Day 22). Assessments are indicated by green circles at each visit, with a red star at Visit 5 marking the primary endpoint. Randomization occurs at Visit 2, splitting subjects into two groups: AXR-270 0.2% (N = 42) and Vehicle (N = 21). Washout periods (W-2, W1, W2, W3) are shown below the treatment bars.
 
Note: Cohort 2 (AXR-270 Cream 2.0% or vehicle) follows the same visit schedule as above and will start enrolling once enrollment of Cohort 1 is complete.

Safety Endpoints:
	
 • Adverse event (AE) • Best corrected visual acuity (BCVA) • Slit-lamp biomicroscopy and external eye exam • Intraocular pressure (IOP) • Dilated ophthalmoscopy • Safety labs (Hematology, clinical chemistry, and urinalysis)

Efficacy Endpoints:
	
All efficacy endpoints are exploratory in nature. The following endpoints will be considered to assess the efficacy of AXR-270 Cream.
 
 1. Change from baseline (Visit 2/Day 1) in the following individual subject-reported symptoms using Visual Analog Scale (VAS, 0-100 point scale) score in the AXR-270 Cream (0.2% or 2.0%) arms compared to Vehicle at Day 22: 
 ○ Eye Discomfort ○ Eye Dryness 2. Change from baseline in Investigator-rated signs of MGD using individual severity scores in AXR-270 Cream arm compared to Vehicle at Day 22: 
 ○ Total MGD Score: the sum of secretion in 5 central glands on each individual eyelid will be evaluated, each will be scored from 0-3; 0 = clear/slightly yellow, 1 = opaque/yellow, whitish, particulate, 2 = paste, 3 = none/occluded; total score will range from 0-15

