5.1. VISIT DESCRIPTIONS

NOTE: In light of the Coronavirus Disease 2019 (COVID-19) pandemic, the site should utilize risk mitigation techniques for all in-clinic visits as described by the American Academy of Ophthalmology (Appendix 17).

5.1.1. Visit 1 (Screening): Day minus 14 (± 2 days) prior to Visit 2

The following will be performed/assessed in the order suggested below and in both eyes:

- Explain the purpose and conduct of the study to the subject, answer the subject's questions, and obtain written informed consent.
- Obtain information including demographics, concomitant medications, ocular and systemic medical and medication history and surgical history.*
- Evaluate eligibility
- A Screening Identification (ID) should be assigned to the Subject once any Visit 1 procedures (other than ICF) are performed. The Subject ID format will be XXX-001 where XXX represents the site number and the last three digits represent the unique subject number.
- Subject-rated symptom assessments (in this order):
 - Individual Symptom Assessment via VAS
 - OSDI
 - Modified BLISS
- Urine Pregnancy Test (UPT) for all eligible women of childbearing potential. *
- For subjects presenting at Visit 1 or Visit 2 with makeup applied to the eyelids or eyelashes, subjects should use a Sponsor provided lid scrub to remove the makeup. (Subjects may resume using makeup between study visits but not on the day of a study visit). Study specific testing related to the evaluation of the eye and eyelids should start 15 minutes after makeup removal.
- For subjects presenting at any post-randomization visit with makeup applied to the eyelids or eyelashes, the site staff should use the Sponsor provided lid scrub to remove the eyelid makeup. Care should be taken not to aggressively clean the lid

margin with the lid scrub and only to gently remove any remaining makeup from the skin surface.

- BCVA
- Slit-lamp biomicroscopy and external eye exam
- TBUT
- FCS
- Investigator-rated assessment of MGD (in both eyes for upper and lower lids)
 - See Appendix 3. Assessment of Efficacy for full description of Investigator-rated assessments for objective signs of change from baseline
- LGS (at a subset of sites)
- Wait 15-20 minutes after LGS before proceeding
- Unanesthetized Schirmer test
- IOP
- Dilated Ophthalmoscopy

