APPENDIX 8: EYE DISCOMFORT, EYE DRYNESS SYMPTOM ASSESSMENT

Symptom Assessment Visual Analog Scale (VAS)

Subjects will be asked the following questions regarding their current symptoms (unrelated to Investigational Product instillation) at each visit.

The subject will be asked to subjectively rate each ocular symptom (OU) by placing a vertical mark on the horizontal line to indicate the level of eye discomfort and dryness. 0 corresponds to “No Symptoms” and 100 corresponds to “Severe Symptoms”

Subject Instructions: Please review the symptoms below. After your review, please rate how your eyes feel for each of the following symptoms by placing a single vertical mark that represents how your symptom feels at this moment.

0 = No Symptoms and 100 = Severe Symptoms

Eye Discomfort	0	100

Eye Dryness	0	100

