2.4. Study Procedures

The schedule of assessments, as outlined in the study protocol, is provided in Table 1.

Statistical Analysis Plan Template

Sponsor:	AxeroVision, Inc.		
Protocol:	AXR201901		
Document Version No.:	1.1	Document Date:	26-OCT-2020

Table 1 Schedule of Assessments

Procedures	Visit 1	Visit 2	Visit 3	Visit 4	Visit 5
	Day minus 14 (±2 days)	Day 1	Day 8 (±2 days)	Day 15 (±3 days)	Day 22 (±3 days)
	Screening	Randomization	Week 1	Week 2	Week 3
	Equalization Period	Treatment Period			Study Termination
Informed Consent	X				
Inclusion/Exclusion Criteria	X	X			
Randomization Criteria		X			
Demographics, Systemic and Ocular Medical History	X				
Subject-rated Symptom Assessments VAS (Eye Discomfort and Eye Dryness)	X	X	X	X	X
OSDI	X	X	X	X	X
Modified BLISS	X	X	X	X	X
Concomitant Medication Query	X	X	X	X	X
Adverse Event Query		X	X	X	X
UPT	X				X
BCVA	X	X	X	X	X
Slit-lamp Biomicroscopy (including External Eye Exam)	X	X	X	X	X
TBUT	X	X	X	X	X
FCS	X	X	X	X	X
Investigator-rated assessment of signs of MGD: Total MGD Score Eyelid margin vascularity Bulbar conjunctival hyperemia	X	X	X	X	X
LGS ^a	X	X	X	X	X
Unanesthetized Schirmer Test	X	X	X	X	X
IOP	X	X	X	X	X
Dilated Ophthalmoscopy	X				X
Safety Lab Draw		X			X

Statistical Analysis Plan Template

Sponsor:	AxeroVision, Inc.		
Protocol:	AXR201901		
Document Version No.:	1.1	Document Date:	26-OCT-2020

	Visit 1	Visit 2	Visit 3	Visit 4	Visit 5
Procedures	Day minus 14 (±2 days)	Day 1	Day 8 (±2 days)	Day 15 (±3 days)	Day 22 (±3 days)
	Screening	Randomization	Week 1	Week 2	Week 3
	Equalization Period	Treatment Period			Study Termination
Dispense Investigational Product for Home Administration		X			
Dispense Daily Dosing Diaries / IP Comfort Assessment Questionnaire		X			
In Clinic Administration of Investigational Product, IP Comfort Assessment Questionnaire and Instruction on Proper Administration ^b		X			
Collect/Review Daily Dosing Diary, IP Comfort Assessment Questionnaire and Investigational Product			X ^c	X	X
Study Termination					X

Key: OSDI=Ocular Surface Disease Index; TBUT=Tear Break up Time; BLISS= BLEpharItIS Symptom; AE=Adverse Event; UPT=Urine Pregnancy Test; IOP=Intraocular Pressure; VAS=Visual Analog Scale; BCVA=Best Corrected Visual Acuity; FCS=Fluorescein Corneal Staining; LGS=Lissamine Green Staining; IP=Investigational Product.

^aOnly to be performed at a subset of sites
^bIncludes dosing video on proper administration of IP
^cIP will not be collected at Visit 3

Sponsor:	AxeroVision, Inc.		

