4.2. General Statistical Methods and Data Handling

4.2.1. General Methods

All output will be incorporated into Microsoft Excel or Word files, sorted and labeled according to the International Conference on Harmonisation (ICH) recommendations, and formatted to the appropriate page size(s).

Tabulations will be produced for appropriate demographic, baseline, efficacy, and safety parameters. Baseline is considered to be the last assessment prior to first dose. For categorical variables, summary tabulations of the number and percentage within each category (with a category for missing data) of the parameter will be presented. For continuous variables, the mean, median, standard deviation, minimum and maximum values will be presented.

Formal statistical hypothesis testing will be performed on the VAS scores, Total MGD score, eyelid margin vascularity, LGS grade, conjunctival hyperemia, Schirmer score, TBUT, FCS, and OSDI with all tests conducted at the 2-sided, 0.05 level of significance. Summary statistics will be presented, as well as confidence intervals on selected parameters, as described in the sections below.

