 - Total MGD Score: the sum of secretion in 5 central glands on each individual eyelid will be evaluated, each will be scored from 0-3; 0 = clear/slightly yellow, 1 = opaque/yellow, whitish, particulate, 2 = paste, 3 = none/occluded; total score will range from 0-15
 - Vascularity of eyelid margin (Grade 0-4)
3. Change from baseline in average TBUT in AXR-270 Cream arms compared to Vehicle at Day 22. (TBUT is the number of seconds that elapse between the last blink and the appearance of the first dry spot in the tear film)

Sponsor:	AxeroVision, Inc.		
Protocol:	AXR201901		
Document Version No.:	1.1	Document Date:	26-OCT-2020

4. Change from baseline in upper lid horizontal length staining, longest sagittal width of staining, and LGS score of the eyelid margin in AXR-270 Cream arms compared to Vehicle at Day 22
5. Change from baseline in tFCS score (NEI/Industry Workshop; 0-15 scale) in the AXR-270 Cream arms compared to Vehicle at Day 22
6. Change from baseline in FCS (0-3 scale) by individual region (5 zones) in AXR-270 Cream arms compared to Vehicle at Day 22
7. Change from baseline in bulbar conjunctival hyperemia (0-4 scale) in AXR-270 Cream arms compared to Vehicle at Day 22
8. Change from baseline in OSDI score (0-100) in AXR-270 Cream arms compared to Vehicle at Day 22
9. Change from baseline in the modified BLISS score in AXR-270 Cream arms compared to Vehicle at Day 22
10. Change from baseline in the Schirmer score in AXR-270 Cream arm compared to Vehicle at Day 22

VAS scores, Total MGD score, eyelid margin vascularity, LGS grade, conjunctival hyperemia, Schirmer score, TBUT, FCS, and OSDI of the study eye/eyelid will be analyzed as continuous data. Analysis will be performed at each timepoint for the value at that timepoint and change from baseline using summary statistics. Change from baseline will also be analyzed with a longitudinal model with terms for baseline value and treatment.

The study eye/eyelid is the eye with the eligible eyelid having the worst (higher) score defined as the sum of the following two severity scores for the clinical signs of MGD at baseline:

1. Vascularity of eyelid margin
2. Total MGD Score

If both eyes, and eyelids, are eligible and have the same score, then select the right eye and upper eyelid. The non-study eyelid will only be the other eyelid(s) that meet all the eligibility rules that the study eyelid met as defined below.

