A study eye/eyelid is eligible if Inclusion Criteria #3, Inclusion Criteria #5, and Exclusion Criteria #3 are met for the same eyelid at Visit 1 and Visit 2.

Inclusion Criteria #3: Have a clinical diagnosis of moderate to severe MGD and who meet both of the following criteria, in at least one qualifying eyelid (upper and lower eyelid for each eye will be evaluated independently), at both Visit 1 (Screening) and again in the same eye/eyelid at Visit 2 (Randomization) examinations:

Sponsor:	AxeroVision, Inc.		
Protocol:	AXR201901		
Document Version No.:	1.1	Document Date:	26-OCT-2020

- a) Total MGD Score ≥ 5 and ≤ 14 (the sum of the individual score of 5 central glands on the upper and lower eyelids will be evaluated, each will be scored from 0-3: 0 = clear/slightly yellow, 1 = opaque/yellow, whitish, particulate, 2 = paste, 3 = none/occluded; total score will range from 0-15).
- b) Clinical sign severity score of at least 2 (moderate) on vascularity of the eyelid margin

Inclusion Criteria #5: Meet the following criteria, in both or the same qualifying eye as in Inclusion #3, at both Visit 1 (Screening) and Visit 2 (Randomization) examinations:

- a) tFCS score ≥ 3 and ≤ 14 in the NEI/Industry Workshop scale (0-15)
- b) Schirmer score of >7 mm without topical anesthesia

Exclusion Criteria #3: In the study eyelid, have greater than 4 glands that are not expressible from the 5 upper and/or 5 lower eyelid meibomian glands at both Visit 1 and Visit 2.

Least squares means for each treatment group and for the differences between 0.2% AXR-270 Cream and Vehicle, 2.0% AXR-270 Cream and Vehicle, and 0.2% AXR-270 Cream and 2.0% AXR-270 Cream will be presented from each model together with two-sided p-values and 95% confidence intervals at each post-baseline visit. The differences between Day 8 and baseline, Day 15 and baseline, and Day 22 and baseline for each treatment individually will also be presented from the model with two-sided p-values and 95% confidence intervals at each post-baseline visit.

Sample SAS longitudinal model code:

```

PROC MIXED DATA=INDATA;
  BY <EYE> <PARAMETER>; ** include <EYE> as applicable;
  CLASS <TREATMENT> <SUBJECT> <VISIT>;
  MODEL <ENDPOINT>=<TREATMENT> <VISIT> <TREATMENT>*<VISIT> <BASELINE>;
  REPEATED <VISIT> / SUBJECT=<SUBJECT> TYPE=UN;
  RANDOM Intercept;
  LSMEANS <TREATMENT>*<VISIT> / CL ALPHA=0.05;
  ESTIMATE '2.0 - Vehicle @ Day 8' <TREATMENT> -1 0 1
           <TREATMENT>*<VISIT> -1 0 0 0 0 0 1 0 0 /

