           CL ALPHA=0.05;
  ESTIMATE '0.2 - Vehicle @ Day 8' <TREATMENT> -1 1 0
           <TREATMENT>*<VISIT> -1 0 0 1 0 0 0 0 0 /
           CL ALPHA=0.05;
  ESTIMATE '2.0 - 0.2 @ Day 8' <TREATMENT> 0 -1 1
           <TREATMENT>*<VISIT> 0 0 0 -1 0 0 1 0 0 / CL
           ALPHA=0.05;
  ESTIMATE 'Day 8 - Baseline for 2.0' <TIME> -1 0 1
           <TREATMENT>*<TIME> -1 0 1 0 0 0 0 0 0 /
           CL ALPHA=0.05;
RUN;

```

Sponsor:	AxeroVision, Inc.		
Protocol:	AXR201901		
Document Version No.:	1.1	Document Date:	26-OCT-2020

Where <TREATMENT> is sorted in ascending order of 0.2% AXR-270, 2.0% AXR-270, then Vehicle and <VISIT> is sorted in ascending order of Day 8, Day 15, and Day 22.

The variance-covariance structure (TYPE=) will be unstructured (UN). In the event that UN does not converge, then autoregressive (AR(1)) and compound symmetry (CS) will be used in that order until the model converges. A random subject intercept will also be included in the model (using Random INT statement in Proc mixed). An additional BY statement for eye will be added for endpoints that are evaluated by study/non-study eye.

Analysis of the non-study eye/eyelids will also be conducted on each of the above endpoints as supportive analysis.

If any values are missing for the study eye/eyelid, a sensitivity analysis will be conducted where missing values are imputed with the LOCF method.

In addition, time to resolution and responder analysis will be performed for the following efficacy variables:

- Eye Discomfort VAS (6 responder levels)
 - 20%, 30%, 50%, and 100% improvement
 - 10+ points and 15+ points improvement
- Eye Dryness VAS (6 responder levels)
 - 20%, 30%, 50%, and 100% improvement
 - 10+ points and 15+ points improvement
- Study Eyelid Total MGD (2 responder levels)
 - 0 Score
 - 3+ points improvement
- Study Eyelid Margin Vascularity (1 responder level)
 - 1+ step improvement
 - 2+ step improvement
- Study Eye TBUT (2 responder levels)
 - ≥7 seconds
 - ≥10 seconds
- Study Eye LGS Score (2 responder levels)
 - 0 Score
 - 3+ step improvement
- Study Eye tFCS (2 responder levels)
 - 0 Score
 - 3+ step improvement
- Study Eye FCS Central Zone (2 responder levels)
 - 0 Score
 - 1+ step improvement
- Study Eye FCS Inferior Zone (2 responder levels)
 - 0 Score

Sponsor:	AxeroVision, Inc.		
Protocol:	AXR201901		
Document Version No.:	1.1	Document Date:	26-OCT-2020

- 1+ step improvement
- Study Eye FCS Nasal Zone (2 responder levels)
 - 0 Score
 - 1+ step improvement

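### The longitudinal model adjusts only for the Visit 2 value and leaves the pre-randomisation Visit 1 value of the same measures unused, a likely but unquantified loss of precision

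*SAP*

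**What the plan says.** **Two pre-dose measurements.** The schedules in Protocol Appendix 1 and SAP 2.4 (for example the row "Subject-rated Symptom Assessments VAS (Eye Discomfort and Eye Dryness") mark the VAS items, OSDI, modified BLISS, TBUT, FCS, the investigator-rated signs (Total MGD score, vascularity, hyperemia), LGS and Schirmer at both Visit 1 and Visit 2. LGS is done only at some sites. Protocol 5.1.1 has the lid signs graded at Visit 1 for every lid: "Investigator-rated assessment of MGD (in both eyes for upper and lower lids". So a Visit 1 value exists for whichever lid becomes the study eyelid.

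**One baseline.** SAP 4.2.1 says "Baseline is considered to be the last assessment prior to first dose", which is Visit 2. The protocol synopsis agrees: "Change from baseline (Visit 2/Day 1) in the following individual subject-reported symptoms".

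**One covariate.** The SAP 4.6 text reads "Change from baseline will also be analyzed with a longitudinal model with terms for baseline value and treatment". The sample code there has "MODEL <ENDPOINT>=<TREATMENT> <VISIT> <TREATMENT>*<VISIT> <BASELINE>", and its note says "<VISIT> is sorted in ascending order of Day 8, Day 15, and Day 22". Visit 1 is therefore neither a covariate nor an outcome. Within SAP 4.6 it serves only to decide which eyelids are eligible.

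**Context.** SAP 4.2.1 sets two-sided 0.05 tests on these measures. SAP 4.2.4 says that no covariate-adjusted analysis is planned, which already sits badly with the baseline term in 4.6. Modified BLISS is categorical (SAP 2.5.1) and outside this model.

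**The concern.** A single pre-dose reading measures a subject's underlying level with error. The VAS, for instance, asks for one mark: "placing a single vertical mark that represents how your symptom feels at this moment". For the lid scores, the study eyelid is chosen as the worst-scoring eligible lid at baseline, so its Visit 2 score tends to be high partly by chance. A second pre-randomisation reading of the same measure can explain some of the outcome variation that the first leaves over. If it does, every between-arm interval from the model narrows without new data.

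Each contrast against Vehicle compares about 42 subjects with about 42 (SAP 2.1; Vehicle pooled under 4.2.3). The SAP reports intervals and p-values at every post-baseline visit, so precision bears directly on what the exploratory efficacy results can show.

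**Working it through.** **No plan figure to reproduce.** Protocol 9.6 and SAP 4.1 state that no sample size calculation was done. No SD, effect size, correlation or power is given.

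**Inputs from the documents.** 42 per arm in each contrast (42 + 21 = 63 per cohort; 2 × 63 = 126); two-sided alpha 0.05.

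**Assumptions.** r2 = correlation of Visit 2 with the Day 22 value, r1 = correlation of Visit 1 with Day 22, r12 = correlation of Visit 1 with Visit 2. Reference power with Visit 2 alone is set at 80% or 60% purely as a yardstick. The calculation looks at one post-baseline visit, with unit variance and a normal approximation.

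Subtracting Visit 2 from the outcome while Visit 2 is a covariate only shifts its slope, so the residual variance is the same for change and for the post-baseline value:

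- Visit 2 only: 1 − r2²
- Visit 1 and Visit 2: 1 − (r1² + r2² − 2·r1·r2·r12)/(1 − r12²)
- With all three correlations equal to r, the ratio of the second to the first is (1 + 2r)/(1 + r)²
- Power with both = Φ[(1.96 + z)/√ratio − 1.96], with z = 0.842 for 80% and 0.253 for 60%

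**Case A: equal correlations**

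| r | Visit 2 only | both | ratio | variance cut | from 80% | from 60% | equivalent n per arm (42/ratio) |
|---|---|---|---|---|---|---|---|
| 0.3 | 0.910 | 0.862 | 0.947 | 5.3% | 82.1% | 62.4% | 44.4 |
| 0.4 | 0.840 | 0.771 | 0.918 | 8.2% | 83.2% | 63.7% | 45.7 |
| 0.5 | 0.750 | 0.667 | 0.889 | 11.1% | 84.4% | 65.1% | 47.2 |
| 0.6 | 0.640 | 0.550 | 0.859 | 14.1% | 85.6% | 66.5% | 48.9 |
| 0.7 | 0.510 | 0.424 | 0.830 | 17.0% | 86.7% | 68.0% | 50.6 |

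Standard errors shrink by 2.7% (r = 0.3) to 8.9% (r = 0.7).

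**Case B: Visit 1 correlates 0.1 less with Day 22** (r12 = r2, r1 = r2 − 0.1)

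| r2 | Visit 2 only | both | variance cut | from 80% | from 60% |
|---|---|---|---|---|---|
| 0.5 | 0.750 | 0.720 | 4.0% | 81.6% | 61.8% |
| 0.6 | 0.640 | 0.609 | 4.8% | 81.9% | 62.1% |
| 0.7 | 0.510 | 0.486 | 4.7% | 81.8% | 62.0% |

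**Case C: Visit 1 adds nothing given Visit 2** (r1 = r2·r12, as under AR(1)-type decay). For r2 = r12 = 0.6 and r1 = 0.36, both variances are 0.640. The gain is zero, and the extra degree of freedom costs about 120/119 = 1.008, or 0.8% in variance.

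**Entry thresholds at both visits.** Protocol 4.1 selects on Total MGD score, vascularity, Discomfort VAS, tFCS, Schirmer and OSDI at both visits, which weakens the correlations. In simulations that kept subjects above the 20th or 40th percentile at both visits, with r = 0.5 to 0.7 before selection, the Case A cut becomes about 6 to 14% (2.5 to 5.4 points from 80%). The Case B cut becomes about 2 to 4% (0.9 to 1.4 points from 80%, up to 1.6 from 60%). Vascularity has only grades 2, 3 and 4 left after entry, so a percentile cut describes it poorly.

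**Averaging the two visits is not a safe substitute.** With r2 = r12 = 0.6 and r1 = 0.36, the mean correlates (0.6 + 0.36)/√(2 + 1.2) = 0.537 with the outcome. Residual variance is then 1 − 0.288 = 0.712 against 0.640, a rise of 11%, and 80% power falls to 75.7%.

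**The case against.** **Visit 2 may simply be the better covariate.** It follows a 14-day Equalization Period whose stated purpose (Protocol 1.2) is to make baseline conditions comparable. Visit 1 precedes the change in lid hygiene, may follow only 2 days off artificial tears, and lies two weeks further from Day 22. Case A may therefore be too favourable. This stands, and it is why the range runs down to zero. It does not make Visit 1 improper as a covariate: the value is pre-randomisation, so these differences can reduce the gain but cannot bias the treatment contrast.

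**A reader might infer that Visit 2 is the noisier reading.** The documents do not support that. The VAS wording is the same at both visits. The worst-lid argument covers only the lid scores, and the Visit 1 lid score is also selected, because the same lid must qualify at both visits. What can be said is that one reading is used where two exist.

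**No power target is missed.** The primary objective is safety and tolerability, efficacy is exploratory, and Protocol 9.7 calls p-values descriptive. This stands as to weight. It does not make precision irrelevant, since estimates and intervals are what the efficacy part delivers.

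**Scope is limited.** Modified BLISS, the responder analyses and time to resolution would not change. LGS gains only where it is collected.

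**Conclusion.** The omission is real and its cost is uncertain. Every measure in the longitudinal model has an unused pre-randomisation value. Using it would cut residual variance by about 5 to 17% under assumed equal correlations of 0.3 to 0.7, by about 4 to 5% if Visit 1 is 0.1 less correlated with Day 22, and by nothing if Visit 1 is uninformative given Visit 2. In power terms that is 0 to about 7 points from an 80% yardstick and up to 8 from 60%, with less for the thresholded measures, Schirmer among them.

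Two stronger readings are tempting and should not be drawn. The planned model is not biased or invalid: it is a proper single-baseline analysis consistent with the protocol's definition of baseline. Nor can it be said that every interval is wider than it need be, because that depends on correlations the documents do not report. The single-visit calculation is also a simplification, since the SAP model fits one baseline slope across Days 8, 15 and 22.

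**What to change.** Before unmasking, amend SAP 4.6:

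- Keep change from Visit 2 as the response and keep the Visit 2 value as a covariate.
- Add the Visit 1 value of the same measure, for the same eye or lid, as a second covariate. In the sample code this is one further term, `<SCREENING>`, after `<BASELINE>` in the MODEL statement. Apply it to every endpoint in the longitudinal model.
- Do not replace Visit 2 by the mean of the two visits.
- If the Visit 1 value is missing, use the subject's Visit 2 value. This should be rare, because most of these measures are needed for entry.
- Reword SAP 4.2.4 so that it no longer rules out covariate adjustment and names the baseline terms used in 4.6.

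The cost is one covariate in text and code, one degree of freedom (about 0.8% in variance at worst) and a one-line missing-value rule. No new data are needed, and the endpoint and reference visit stay as they are.

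### In the SAP's sample model code, the three between-arm ESTIMATE statements do not return the comparisons on their labels under the stated treatment order, and the fourth uses an effect that is not in the model

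*SAP*

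**What the plan says.** SAP 4.6 plans a longitudinal model of change from baseline. The text promises: "Least squares means for each treatment group and for the differences between 0.2% AXR-270 Cream and Vehicle, 2.0% AXR-270 Cream and Vehicle", and also 0.2% against 2.0%, with two-sided p-values and 95% confidence intervals at each post-baseline visit.

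The sample code has treatment, subject and visit as class variables. Its fixed effects are treatment, visit, their interaction and the baseline value. The between-arm statements, each followed by nine interaction coefficients, begin:

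- "ESTIMATE '2.0 - Vehicle @ Day 8' <TREATMENT> -1 0 1"
- "ESTIMATE '0.2 - Vehicle @ Day 8' <TREATMENT> -1 1 0"
- "ESTIMATE '2.0 - 0.2 @ Day 8' <TREATMENT> 0 -1 1"

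A fourth statement is meant to give the within-arm change: "ESTIMATE 'Day 8 - Baseline for 2.0' <TIME> -1 0 1".

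The text after the code sets the level order: "Where <TREATMENT> is sorted in ascending order of 0.2% AXR-270, 2.0% AXR-270, then Vehicle". It sets the visit order as Day 8, Day 15, Day 22.

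The least-squares-means statement is "LSMEANS <TREATMENT>*<VISIT> / CL ALPHA=0.05", with no option for differences. SAP 4.2.1 lists these variables for formal testing, "with all tests conducted at the 2-sided, 0.05 level of significance".

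**The concern.** ESTIMATE coefficients apply to class levels by position, so a label is true only if the levels sort in the order the coefficients assume. These coefficients treat Vehicle as the first level, whereas the SAP puts it last.

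In this code the ESTIMATE statements are the only source of the promised between-arm differences, intervals and p-values. Only Day 8 is shown, so a programmer must extend the pattern to Day 15 and to Day 22, the endpoint visit. The three between-arm statements are internally coherent. Once the fourth is removed they would run without error and print well-formed but mislabelled results. The stated order is also the alphanumeric order of the arm names as written, so an ordinary sort would not correct the mismatch. The risk is that an effect, or its absence, is attributed to the wrong dose.

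**Working it through.** **Inputs (all SAP 4.6).** Treatment levels: 1 = 0.2%, 2 = 2.0%, 3 = Vehicle. Visit levels: Day 8, 15, 22. From the order of the class variables, visit varies fastest in the interaction, so cells 1–3 are 0.2%, cells 4–6 are 2.0% and cells 7–9 are Vehicle, each at Day 8, 15, 22. There is no sample-size or power figure to reproduce; what has to be reproduced is each label.

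**Formula.** A statement with interaction coefficients c₁…c₉ returns Σ cₖμₖ, where μₖ is the cell LS mean. This requires that the coefficients summed over visits within each treatment equal the main-effect coefficients, and that those summed over treatments within each visit are zero. Both conditions hold for the three between-arm statements.

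**Result under the stated order (Day 8)**

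| Label | Main effect | Non-zero interaction cells | Returns |
|---|---|---|---|
| 2.0 − Vehicle | −1 0 1 | −1 on cell 1, +1 on cell 7 | Vehicle − 0.2% |
| 0.2 − Vehicle | −1 1 0 | −1 on cell 1, +1 on cell 4 | 2.0% − 0.2% |
| 2.0 − 0.2 | 0 −1 1 | −1 on cell 4, +1 on cell 7 | Vehicle − 2.0% |

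None of the three labels holds. All three pairs of arms are printed, each under another pair's label.

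**All six orders.** Labels that hold: (0.2, 2.0, Veh) 0; (0.2, Veh, 2.0) 0; (2.0, 0.2, Veh) 0; (2.0, Veh, 0.2) 0; (Veh, 0.2, 2.0) 3; (Veh, 2.0, 0.2) 0.

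**Fourth statement.** It uses `<TIME>`, which is in neither the CLASS nor the MODEL statement. Read as visit, its coefficients are −1 on cell 1 and +1 on cell 3, which is Day 22 minus Day 8 in the 0.2% arm. No order makes it Day 8 minus baseline for 2.0%, because visit has no baseline level and the response is already a change from baseline. The quantity wanted is the 2.0% Day 8 cell LS mean.

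**Illustrations (assumed mean changes; none are in the documents).** Each cell gives printed value / true value of the label.

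| Vehicle, 0.2%, 2.0% | 2.0 − Vehicle | 0.2 − Vehicle | 2.0 − 0.2 |
|---|---|---|---|
| Graded: −10, −15, −25 | +5 / −15 | −10 / −5 | +15 / −10 |
| Low dose inert: −10, −10, −25 | 0 / −15 | −15 / 0 | +15 / −15 |
| Plateau: −10, −25, −25 | +15 / −15 | 0 / −15 | +15 / 0 |

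Example, graded, first row: −10 − (−15) = +5, against −25 − (−10) = −15.

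**Significance rates.** Two-sided two-sample t-test at 0.05, 42 per arm, 82 df, noncentrality d√(42/2), no gain from baseline adjustment, low dose inert:

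| Assumed 2.0% effect (SD) | Row labelled 0.2 − Vehicle (should be 5%) | Row labelled 2.0 − Vehicle | Correct rate for 2.0 − Vehicle |
|---|---|---|---|
| 0.3 | 27% | 5% | 27% |
| 0.5 | 62% | 5% | 62% |
| 0.8 | 95% | 5% | 95% |

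**Scope.** Continuous parameters: VAS 2, Total MGD 1, vascularity 1, TBUT 1, LGS 3 (length, width, score), tFCS 1, FCS regions 5, hyperemia 1, OSDI 1, Schirmer 1 = 17. Then 17 × 3 visits × 3 comparisons = 153 study-eye or subject-level differences in the Full Analysis Set, and 17 × 3 = 51 at Day 22.

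**Secondary point, same code.** With three visits, an unstructured covariance has 6 parameters. Adding a subject intercept makes 7, of which 6 are identifiable. Compound symmetry plus an intercept has 2 of 3 identifiable; AR(1) plus an intercept has 3 of 3. The intercept is therefore redundant under the first choice and under the compound-symmetry fallback. The coded RANDOM statement also has no SUBJECT= option, although the text describes a subject intercept.

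**The case against.** The code is labelled as a sample and uses placeholders, and the prose above it names the right comparisons, so the intended analysis is not in doubt. The coefficients are right for a Vehicle-first order, so the sentence on order may be the slip. That stands, and it makes the between-arm defect cheap to cure. It does not remove the conflict between the code and the sentence that defines its levels.

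The block cannot be run verbatim: the fourth statement fails and Days 15 and 22 must be added. So 153 counts planned contrasts, not expected errors. That is fair. But extending the template in the stated order carries the fault to every visit.

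`<TIME>` may simply be another name for visit. If so, the statement would run, but its coefficients would still be wrong.

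LS means appear beside the differences, so subtraction would expose the mismatch. That is a real safeguard, but only if someone does the check.

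The significance rates rest on assumed effects and on 42 per arm. LGS is done at a subset of sites, so that number does not fit the 3 LGS parameters, which account for 3 × 9 = 27 of the 153 contrasts.

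The random-intercept point is separate from the contrast order, and no effect on an estimate or p-value has been shown. It is kept as secondary.

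**Conclusion.** The concern holds. Under the SAP's own order none of the three between-arm labels is true, and the fourth statement cannot give what its label says under any order. This follows from the code and the order sentence alone; the numerical illustrations show possible consequences and rest on assumed effects.

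The reach is limited. Per-arm LS means, responder tests and time-to-resolution tests do not use these statements. The figure asterisks for treatment against vehicle are affected only if their p-values come from this model, which the SAP does not say. The primary objective is safety and tolerability, efficacy is exploratory, and protocol section 9.7 calls p-values descriptive. Because the SAP nevertheless sets formal 0.05 tests on these variables, this should be fixed before programming.

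**What to change.** Either state the treatment order as Vehicle, 0.2%, 2.0% and sort the data to match, or keep the stated order and replace the coefficients with these:

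| Comparison | Treatment | Day 8 interaction | Day 15 interaction | Day 22 interaction |
|---|---|---|---|---|
| 2.0 − Vehicle | 0 1 −1 | 0 0 0 1 0 0 −1 0 0 | 0 0 0 0 1 0 0 −1 0 | 0 0 0 0 0 1 0 0 −1 |
| 0.2 − Vehicle | 1 0 −1 | 1 0 0 0 0 0 −1 0 0 | 0 1 0 0 0 0 0 −1 0 | 0 0 1 0 0 0 0 0 −1 |
| 2.0 − 0.2 | −1 1 0 | −1 0 0 1 0 0 0 0 0 | 0 −1 0 0 1 0 0 0 0 | 0 0 −1 0 0 1 0 0 0 |

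Delete the fourth ESTIMATE and take within-arm change from the treatment-by-visit LS means. As a secondary edit, drop the RANDOM statement under the unstructured and compound-symmetry structures; if an intercept is kept under AR(1), add `SUBJECT=<SUBJECT>`.

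The cost is SAP wording and sample code only. Neither the data nor the sample size is affected.
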